1. Testing of serum specimens for this study will be performed in batches.
 - a. Negative results are final.
 - b. Positive results are retested on the next work-day for confirmation. If original test is performed on Friday, repeat testing of positive specimens will be performed the following Monday.
2. Testing will not occur under the following conditions:
 - a. The specimen stored under unacceptable storage times and/or temperatures.
 - b. The specimen has been shipped under unacceptable time and/or temperature conditions

- c. The specimen volume is less than needed to complete the testing process.
 - d. The specimen cannot be pipetted due to viscosity.
 - e. The specimen is hemolyzed or icteric
 - f. The specimen is of a type other than serum separated off the clot.
3. If a specimen is received and falls under one of the five criteria listed above, a call will be made to the study site to inform them that testing on the specimen could not be performed.
 4. Fungitell® beta-D glucan Assay results are reported as pg/mL.

13.5.7 Laboratory of Mycology Research key personnel:

Technical Assistance:

[name]

[contact]

[contact]

Director: [name], [contact]

Testing will be performed by technicians blinded to each patient's clinical information. **Test results will not be made available to treating physicians since the utility of these tests is not yet established in children and because we will not be conducting testing in real time. Thus, results will not be utilized for clinical decision-making.**

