To our knowledge BG testing is not routinely performed at many pediatric centers but may be performed at some of the COG sites. Regardless of the number of institutions offering such BG testing, we anticipate that such testing will be ordered by a subset of treating physicians. The local BG results will not be included in our final analysis of the biomarker assay's operating characteristics. However, these results may effect a change from fungal prophylaxis to preemptive or empiric therapy and may encourage or discourage more comprehensive efforts to diagnose a proven or probable IFI in any given patient. This in turn may falsely influence our evaluation of the Fungitell beta-D-glucan Assay's operating characteristics. For each patient we will identify whether local BG testing has been performed and, via a sensitivity analysis, explore whether such a practice influences the operating characteristics. The plans for this sensitivity analysis are described in more detail in Section 13.9.4 below.

The Fungitell beta-D-glucan Assay is reported in pg/ mL of patient's serum. The manufacturer recommendation for a single positive Fungitell Assay result of > 80 pg/mL will be used to define a positive test.

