In the proposed parent trial included patients will be the recipients of allogeneic stem cells (bone marrow, peripheral blood stem cells, or umbilical cord blood). These HCT patients are those at high-risk for an IFI and thus the anticipated incidence rate of IFI may be higher than that reported in the above referenced adult trial. Alternatively, the proposed trial will only follow patients for 100 days from transplantation and thus later onset IFI will not be identifiable. Considering the data presented above and the proposed study parameters, the COG parent trial has conservatively estimated that the IFI incidence rate will be 7% (20 events) in the azole treatment arm and 2% (6 events) in the caspofungin study arm. Because this ancillary study plans to enroll 70% (400 patients) of the parent trial patients over a three-year period the estimated event rates for the azole and caspofungin arms are 14 and 4 respectively (table 3).

| | Total | Azole Arm | Caspofungin Arm |
|------------|-------|-----------|-----------------|
| Number | 400 | 200 | 200 |
| IFI Rate | 4.6% | 7.0% | 2.0% |
| IFI Events | 18 | 14 | 4 |

13.9.2 Sensitivity, Specificity, PPV, and NPV:

The validity of a biomarker is based on whether the study appropriately categorizes patients with and without the illness in question (sensitivity and specificity). Alternatively the validity of a test can be measured by how well the test results predict the presence or absence of the disease (PPV and NPV). Collectively, sensitivity, specificity, PPV, and NPV are often referred to as the test's operating characteristics. Each component of the operating characteristics will be calculated based first on the entire cohort. As indicated in the estimates above, the incidence of is expected to vary between the two study arms. It is well documented that variations in the incidence/prevalence of a disease will impact the operating characteristics of a diagnostic test specifically for the PPV and NPV. Therefore, each assay's sensitivity, specificity, PPV and NPV will also be calculated separately for each study arm.

The operating characteristics for the Fungitell beta-D-glucan Assay will be computed as follows:

- Outcome of all IFI defined as a single positive test for the Fungitell beta-D-glucan Assay as compared to the EORTC/MSG criteria for all proven or probable IFI.

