Sensitivity, specificity, PPV and NPV and their accompanying 95% confidence intervals will be calculated using STATA statistical software version 12.0 (College Station, TX). As noted above, these parameters will first be calculated for the entire cohort and then for each study arm separately. A patient with multiple episodes of IFI will only be included in the analyses as a single IFI. As would be expected in the setting of low incidence, we anticipate that the results will show a low PPV and high NPV. This will not be an indication that the assay is not useful. The intended goal of the assay is to identify all patients with IFI at the earliest time point. In order to identify all such patients there will need to be a tolerance for a certain number of false positive results. Thus in this clinical setting the sensitivity of these assays is the most relevant parameter assuming the number of false positive results is not excessive.

13.9.3 Receiver Operator Characteristics Curve:

In addition to understanding the operating characteristics of a diagnostic test at a single defined threshold, it is also important to understand how variations in the test's threshold can alter the test's operating characteristics. The receiver operating characteristics (ROC) curve is a useful approach to illustrate how these operating characteristics will change as the threshold changes. Therefore, a receiver-operating-characteristics (ROC) curve will be generated with a series of sensitivities and specificities derived from various cutoff values. For the Fungitell Assay cutoffs of ≥ 60 , ≥ 80 , ≥ 100 , and ≥ 120 pg/mL will be used to create the ROC. The ROC curve will be displayed graphically (sensitivity vs. 1-specificity) and evaluated numerically (c-statistic). The c-statistic (also referred to as the area under the curve (AUC)) varies from 0.5 to 1.0 and is a measure of the test's ability to discriminate between patients with and without the gold standard diagnosis.²¹ A c-statistic of 0.5 is possible by chance alone while a perfectly discriminating test will result in a c-statistic of 1.0.

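### The beta-D-glucan ROC curve and c-statistic are built from four cut-offs although continuous pg/mL values are available, so the c-statistic is likely to be understated

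*Combined protocol and SAP*

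**What the plan says.** Section 13.9.3 states that "a receiver-operating-characteristics (ROC) curve will be generated with a series of sensitivities and specificities derived from various cutoff values" and then fixes the list: "For the Fungitell Assay cutoffs of ≥ 60 , ≥ 80 , ≥ 100 , and ≥ 120 pg/mL will be used to create the ROC". The same paragraph continues: "The ROC curve will be displayed graphically (sensitivity vs. 1-specificity) and evaluated numerically (c-statistic". It equates the c-statistic with the area under the curve and says that it "is a measure of the test's ability to discriminate between patients with and without the gold standard diagnosis".

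The raw data are finer than this. Section 13.5.5 records that "beta-D glucan Assay results are reported as pg/mL".

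Later in 13.9.3 the same curves serve an exploratory search for a threshold that favours sensitivity while keeping specificity reasonable. Section 13.7.1 announces a post hoc look at several cut-offs and points to this statistical section for it. Nowhere does the plan provide for a c-statistic from the full range of values, for a smoothed (for example binormal) curve, or for a per-patient summary such as the maximum of the weekly values.

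**The concern.** Four cut-offs turn a continuous measurement into five ordered classes. A case and a non-case in the same class count as a tie, worth one half, even where their pg/mL values separate them clearly. The two outer classes are the widest. On the plan's own healthy-child figure of 22% above 60 pg/mL, about 78% of single non-case values would fall into the lowest class.

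Two outputs are at stake. The c-statistic is the plan's overall measure of discrimination, and section 13.10 expects clinicians not to order the assay if it performs poorly. The threshold search draws on the same curves. Section 13.1.3 says that baseline levels in healthy children point to a higher positivity threshold for children, so the search should not be held back by where a short list of cut-offs happens to stop.

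**Working it through.** **Inputs from the documents.** Cut-offs 60, 80, 100 and 120 pg/mL (13.9.3). Healthy children: 22% above 60 and 15% at or above 80 pg/mL (13.7.1). Up to seven weekly samples (13.4). Hypothesised sensitivity above 90% before diagnosis (13.2); pooled sensitivity 77% in the cited meta-analysis (13.1.3). Expected events (Table 3): "IFI Events | 18 | 14 | 4".

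**The plan's figure.** 200 × 0.07 + 200 × 0.02 = 14 + 4 = 18 events among 400 patients. This reproduces. The plan gives no expected c-statistic.

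**Non-case distribution (assumed lognormal).** The upper 22% and 15% normal points are 0.772 and 1.036.
- Log-SD = ln(80/60) / (1.036 − 0.772) = 1.09.
- Log-mean = ln 60 − 0.772 × 1.09 = 3.25, so the median is 25.9 pg/mL.

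**One worked example.** Take one value per patient, equal log-SD, and sensitivity 77% at 80 pg/mL.

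| Cut-off (pg/mL) | False-positive rate | Sensitivity |
|---|---|---|
| 120 | 0.079 | 0.643 |
| 100 | 0.107 | 0.703 |
| 80 | 0.150 | 0.770 |
| 60 | 0.220 | 0.842 |

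The trapezoids through (0,0), these four points and (1,1) have areas 0.026 + 0.019 + 0.032 + 0.056 + 0.718 = 0.851. The full area is Φ[(5.19 − 3.25) / (1.09 × √2)] = 0.895. The shortfall is 0.045. At 90% sensitivity the values are 0.914 against 0.949, a shortfall of 0.035.

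Across case sensitivities of 60% to 95% and case log-SDs of 0.7 to 1.5, still with one value per patient, the shortfall was 0.023 to 0.066 and never reversed.

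**Repeated samples.** Each patient is scored by the maximum value. Assumptions: within-patient correlation 0.3 or 0.6, cases shifted by 0.8 to 2.0 log units, 200,000 simulated patients per group.

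| Samples per case / non-case | Correlation | Full area | Four-point area | Shortfall | False-positive rate at 120 |
|---|---|---|---|---|---|
| 7 / 7 | 0.3 | 0.75–0.96 | 0.71–0.82 | 0.04–0.14 | 35% |
| 7 / 7 | 0.6 | 0.73–0.93 | 0.70–0.85 | 0.03–0.08 | 26% |
| 4 / 4 | 0.3 | 0.74–0.95 | 0.72–0.86 | 0.03–0.08 | 24% |
| 4 / 4 | 0.6 | 0.72–0.93 | 0.69–0.87 | 0.03–0.06 | 20% |
| 3 / 7 | 0.3 | 0.61–0.90 | 0.59–0.79 | 0.02–0.10 | 35% |
| 3 / 7 | 0.6 | 0.63–0.89 | 0.61–0.82 | 0.02–0.07 | 26% |

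Within every row the shortfall grows with the case shift, that is, as the assay improves. In the seven-sample settings where sensitivity at 80 pg/mL exceeds 90%, it is 0.06 to 0.14. Specificity at the highest listed cut-off is then 65% to 74%.

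**At the planned size.** With 18 cases and 382 non-cases (3,000 runs per setting, one sample or seven independent samples per non-case, one value per case), the mean shortfall was 0.035 to 0.106. The four-point value was the lower one in 97% to 99.97% of runs.

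**The case against.** The direction is conditional. No joining rule is stated, and a smoothed fit could avoid the bias. The sign can also reverse: one setting, with an assay worse than chance (full area 0.44), gave +0.010. This stands, and the conclusion is worded accordingly. But the plan specifies no such fit, and a usefully discriminating assay would normally have a near-concave curve.

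The size is uncertain. Two percentages from healthy children stand in for transplant recipients, and the shape, the correlation and the case shift are assumed. Seven samples is a ceiling: outpatient testing is done when possible, and the limit of 3 mL/kg in eight weeks rules out 7 × 5 = 35 mL below 35/3 = 11.7 kg. Cases scored before diagnosis will have fewer samples still. The retesting of positive results is not modelled. All of this stands, so the three- and four-sample rows are the better guide. The 0.14 is a corner case in which sensitivity at 80 pg/mL is close to 100%.

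Precision is poor in any case. With 18 events the Hanley-McNeil standard error is 0.034 to 0.069 in the eight seven-sample settings, and in five of them the shortfall is smaller than the 95% half-width. That limits the consequence, but it does not justify adding an avoidable systematic error.

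Three stronger readings are tempting, and the documents do not support them.
- *Half of the specificity axis goes unobserved.* A false-positive rate of 26% to 35% at 120 pg/mL leaves about a quarter to a third unobserved.
- *A threshold above 120 pg/mL can never be chosen.* The search is exploratory, section 13.7.1 foresees a post hoc look at cut-offs, and the stated priority is sensitivity. Section 13.1.3 asks for a higher threshold in children but does not say higher than 120.
- *The ancillary study's main result is compromised.* The hypothesis concerns sensitivity, which 13.9.2 ranks as the most relevant measure, and it is assessed at 80 pg/mL. No decision rule uses the c-statistic.

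**Conclusion.** The point holds as an improvement available at no cost, of minor severity. As written, the plan discards information that it already holds. With linear joining and a concave true curve, it would report a c-statistic that is too low by about 0.02 to 0.10 when cases contribute three or four samples, and by up to 0.14 in the extreme seven-sample setting. These figures rest on lognormal values fitted to healthy children, correlation 0.3 to 0.6 and case shifts of 0.8 to 2.0 log units. They are a range, not an estimate for this trial. If patients do give seven samples, the threshold search may end at the edge of the listed grid. Sensitivity, specificity, PPV and NPV at 80 pg/mL are unaffected, as is the primary comparison of caspofungin with azoles.

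**What to change.** Amend section 13.9.3 as follows.

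1. Compute the ROC curve and c-statistic from each patient's maximum continuous pg/mL value. For IFI cases use only samples taken before diagnosis, in line with the hypothesis in 13.2.
2. Report the c-statistic with a DeLong or bootstrap 95% confidence interval. Section 13.9.2 promises intervals for sensitivity, specificity, PPV and NPV, but 13.9.3 gives none for the c-statistic.
3. Show 60, 80, 100 and 120 pg/mL as marked points on that curve.
4. Let the exploratory threshold search use the full observed range.
5. Report the number of samples per patient by case status, and note that cases may have fewer. A maximum rises with the number of samples. In the check above (correlation 0.3, case shift 0.8), the full area was 0.75 with seven samples in both groups and 0.61 with three per case against seven per non-case.

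The cost is a change of wording. The values are already measured, so no further samples, assays or patients are needed.

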Additionally, the ROC curves will be used in an exploratory analysis to identify the threshold for the biomarker assay that optimizes the diagnostic test's sensitivity while maintaining a reasonable specificity. The identified thresholds will be used to categorize each patient as "likely to have IFI" and "not likely to have IFI". Once these 2 sub-groups are defined we will calculate the incidence rates of IFI for each sub-group and compare them. Because the anticipated incidence for IFI may be variable between the two study

arms (those receiving an azole and those receiving caspofungin) this approach will have to be done at the level of each study arm. The incidence rates will be compared statistically using Pearson's Chi-square analysis.

Finally, to further explore the ideal utility and interpretation of each biomarker, serial testing results will be explored. For this analysis the Fungitell beta-D-glucan Assay will be considered positive when a patient has 2 consecutive test results ≥ 80 pg/mL. Operating characteristics and ROC curves will be constructed in a similar manner as discussed above.

13.9.4 Sensitivity Analysis:

Sensitivity analyses will be explored for the reasons expressed in Section 13.7.1 and 13.8. The first sensitivity analysis will attempt to identify the direction and magnitude of the bias resulting from the availability of clinical BG testing performed outside of the ancillary study. Such testing has the potential to change the treating clinician's approach for diagnosing an IFI. It is possible that these test results could result in more or less investigation (e.g. radiologic imaging) to identify an IFI, which could ultimately impact on the incidence of identified IFI. Therefore, in addition to calculating the operating characteristics for all patients enrolled, the same operating characteristics will be calculated after excluding all patients that had at least 1 biomarker test result available to the treating clinician.

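### Section 13.9.3 tests IFI incidence across an ROC-chosen beta-D glucan threshold by Pearson's chi-square in each arm; with about 4 caspofungin IFIs the test is unreliable, and no numeric rule limits the choice of threshold

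*Combined protocol and SAP*

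**What the plan says.** Section 13.9.3 lists the candidate thresholds: "cutoffs of ≥ 60 , ≥ 80 , ≥ 100 , and ≥ 120 pg/mL will be used to create the ROC". It then says that "the ROC curves will be used in an exploratory analysis", the aim being to "identify the threshold for the biomarker assay that optimizes the diagnostic test's sensitivity while maintaining a reasonable specificity". No figure is given for an acceptable specificity.

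The chosen value is applied to the same cohort. "The identified thresholds will be used to categorize each patient as" likely or not likely to have IFI, and the incidence in the two groups is compared. Because incidence may differ by treatment, "this approach will have to be done at the level of each study arm". The test is named: "The incidence rates will be compared statistically using Pearson's Chi-square analysis".

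The table in Section 13.9.1 gives the expected yield as total, azole and caspofungin: "IFI Events | 18 | 14 | 4", from 400, 200 and 200 patients. Section 13.9 describes no exact test, hold-out sample, cross-validation or allowance for having chosen the threshold.

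**The concern.** There are two separate difficulties.

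- **Sparse cells.** Pearson's test relies on a large-sample approximation that is poor when expected counts are small. Four events cannot fill two cells adequately, wherever the threshold falls.
- **Same-data selection.** If the threshold is picked partly because it separates IFI from non-IFI patients, a test of that separation in the same patients can look better than it should.

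At stake is how a small p-value would be read. Section 13.7.1 says the cut-off work is meant to find the most suitable value for later use of the assay, and Section 13.10 expects the results to influence care. A nominally significant difference resting on 2 or 3 caspofungin IFIs could be taken as support for a paediatric cut-off.

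**Working it through.** **1. The plan's event counts.** Section 13.9.1 gives 200 patients per arm and IFI rates of 7% and 2%. 200 × 0.07 = 14, 200 × 0.02 = 4, total 18. These reproduce. (18/400 is 4.5%; the printed 4.6% equals the parent trial's 26/560. Nothing here depends on it.)

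**2. Expected cells.** With E IFIs and m positives among 200, the two expected IFI cells are E × m/200 and E × (200 − m)/200.

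- Caspofungin, E = 4: the cells sum to 4, so both are below 5 and the smaller is at most 2. At m = 30 they are 0.6 and 3.4.
- Azole, E = 14: both reach 5 only if the positive share lies between 5/14 = 36% and 9/14 = 64%.

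**3. One worked table.** Take 30 positives (15%) and 2 of the 4 IFIs among them. Pearson's statistic is 200 × (2 × 168 − 2 × 28)² / (4 × 196 × 30 × 170) = 3.92, above 3.84, so p = 0.048. The hypergeometric probabilities of 2, 3 and 4 IFIs among the positives are 0.0966, 0.0107 and 0.0004. Fisher's p is their sum, 0.108. With 0 or 1 IFI among the positives the statistic is 0.72 or 0.32, so Pearson rejects exactly when there are 2 or more. Its true size here is therefore also 10.8%.

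**4. Exact size at a fixed threshold.** Nominal two-sided 5% (the plan states no level), given the number positive:

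| Share positive | 5% | 10% | 15% | 22% | 30% | 40% | 50% | 60% |
|---|---|---|---|---|---|---|---|---|
| Pearson, 4 IFIs | 1.3% | 5.1% | 10.8% | 3.4% | 8.2% | 2.5% | 12.1% | 2.5% |
| Fisher, 4 IFIs | 1.3% | 0.3% | 1.1% | 3.4% | 0.8% | 2.5% | 0.0% | 2.5% |
| Pearson, 14 IFIs | 2.5% | 3.8% | 4.1% | 4.3% | 3.2% | 4.9% | 4.9% | 4.9% |

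Section 13.7.1 supplies the 15% (at 80 pg/mL) and 22% (above 60 pg/mL), from single tests in healthy children; the other shares are assumptions. Repeating the calculation at every count from 10 to 120 positives gives 0.8% to 12.2% with 4 IFIs (mean 4.3%) and 1.7% to 8.5% with 14 (mean 4.6%). The azole maximum is at 79 positives, where Pearson rejects at 2 or fewer (3.8%) or 9 or more (4.8%).

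**5. Adding the choice among four cut-offs.** This was simulated with no association and 200 patients, at least 20,000 data sets per setting. Assumed ever-positive shares at 60/80/100/120 pg/mL were 22/15/10/7%, 30/20/12/8% and 40/30/22/16%. Rejection rates:

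| Choice of cut-off | 4 IFIs | 14 IFIs |
|---|---|---|
| Pearson, 80 pg/mL fixed | 3.2–5.1% | 3.8–4.7% |
| Pearson, best Youden index | 8.5–9.9% | 7.2–8.3% |
| Pearson, best sensitivity with specificity ≥ 80%, ties to lowest cut-off | 3.0–4.3% | 3.5–4.0% |
| Same, ties to highest cut-off | 4.8–9.2% | 4.3–6.8% |
| Fisher, best Youden index | 4.8–5.1% | 5.5–5.7% |

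In the third set of shares, about 6% of data sets had no cut-off meeting the floor; these count as no rejection.

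The floor behaves differently from Youden for a simple reason. Sensitivity cannot rise as the cut-off rises, so the lowest cut-off that meets the floor always attains the best sensitivity, and whether it meets the floor depends only on non-IFI patients. Ties matter because 4 IFIs allow only five values of sensitivity.

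**The case against.** The strongest reply is that little depends on this test. It is labelled exploratory and sits in an optional ancillary study. That study's hypothesis, sensitivity above 90%, is assessed at the prespecified 80 pg/mL with confidence intervals (Sections 13.2 and 13.9.2). Results do not reach treating physicians (Section 13.5). All of this stands and limits the weight of the point.

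A second reply is that, averaged over the number of positives, Pearson's error at a fixed cut-off is near nominal even with 4 IFIs (3.2% to 5.1% above). That is correct. But the analyst will hold one table with a known number of positives, and for that table the error may be 1% or 12%.

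Some stronger readings are tempting, and the documents do not support them:

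- A reader might infer that the p-value must be optimistic. The stated rule is sensitivity subject to acceptable specificity, not Youden, and with a fixed floor and ties to the lowest cut-off there was no inflation.
- A reader might infer error of 20% or more from a free search along the curve. The plan lists four cut-offs and provides for no such search.
- A reader might infer that Pearson's test is equally unsuitable in both arms. With 14 IFIs, sparseness alone does little harm.
- A reader might infer that a separate threshold is chosen in each arm. The per-arm sentence follows the incidence comparison and may refer only to that.

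**Conclusion.** The point holds as a minor one. In the caspofungin arm Pearson's test is poorly suited at any threshold: its size, given the number positive, is about 1% to 12%. This rests on the plan's own expectation of 4 IFIs in 200 and on a 5% two-sided level.

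In the azole arm the size is 2.5% to 4.9% at the shares tabulated up to 60% positive. It reaches 8.5% at one intermediate count, so an exact test would do no harm there either.

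Optimism from choosing the threshold in the same data is possible but conditional: about 7% to 10% under a Youden choice, and about 3% to 10% under an 80% specificity floor, depending on positive shares and tie-breaking. The positive shares are largely assumed. With up to 7 tests per patient the ever-positive share could be much higher than 15% (1 − 0.85⁷ = 68% if tests were independent), but the caspofungin IFI cells would still be below 5. What the plan lacks is a number for acceptable specificity, so nothing limits the choice after the data are seen.

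**What to change.** In Section 13.9.3:

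1. Replace Pearson's test with Fisher's exact test, at least in the caspofungin arm.
2. Either state a numeric specificity floor and a tie rule before the data are seen, or obtain the p-value by permutation that repeats the choice among the four cut-offs. Fisher's test handles the sparse cells but does not by itself allow for the selection.
3. Say whether the threshold is chosen in the pooled cohort or within each arm.
4. Report the chosen threshold as not validated.

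The cost is a few lines of analysis text and code and somewhat less favourable p-values. Fisher's test is conservative with 4 events: at 100 positives even 4 of 4 IFIs above the threshold gives p = 0.121, which is a fair statement of what 4 events can show. No new data or patients are needed.
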